### 2.2 Secondary Outcomes:

1). Evaluate the tolerability profile of the study therapy, analyzing the side effects.  
2). Evaluate the efficacy of the treatment in terms of subjective improvement of urinary symptoms by performing IPPS and SF-36 questionnaires and evaluate the objective improvement of urinary symptoms by performing uroflowmetry before and during treatment (during follow-up visits -up at 1,3,6 and 12 months) by means of ultrasound evaluation of the post-voiding residue, comparing the patients of the 3 study groups (Arm 1, 2 and 3).

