The most notable adverse effects of 5-ARIs are related to sexual function and include decreased libido, erectile dysfunction (ED), and less frequently, ejaculation disorders such as retrograde ejaculation, ejaculation failure, or decreased semen volume [ 21]. Gynecomastia develops in 1-2% of patients.

According to guidelines (EAU), in addition to the two categories of drugs mentioned above, there are also treatments for BPH based on natural extracts (phytotherapy).

Herbal medicines are made from roots, seeds, pollen, bark or fruit. There are single herbal preparations and preparations that combine two or more plants in one tablet. The most used plants are Cucurbita pepo (pumpkin seeds), Hypoxis rooperi (South African star grass), Pygeum africanum (African plum tree bark), Secale cereale (rye pollen), Serenoa repens (dwarf palm) and Urtica dioica (roots of 'nettle). In vitro, plant extracts may have anti-inflammatory, anti-androgenic and estrogenic effects; they can inhibit aromatase, lipoxygenase, growth factor-stimulated proliferation of prostate cells,  $\alpha$ -adrenoreceptors, 5 $\alpha$ -reductase, muscarinic cholinoreceptors, dihydropyridine and vanilloid receptors, and neutralize free radicals [25-26]. Pharmacokinetic properties can vary significantly depending on how Serenoa repens is extracted.

Herbal therapeutic agents are a heterogeneous group and may contain different concentrations of active ingredients. In general, no herbal agent has been shown to reduce prostate size and a decrease in the progression of BPH has not been demonstrated [27-28]. Side effects during herbal medicine

are usually mild and comparable to placebo. Gastrointestinal disturbances are the most common reported.

Short-term studies have recently been performed on the combination of plant extracts with alpha-blockers and 5-ARIs.

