## 2. Objectives of the study

The objective of this study is to evaluate the efficacy of the PEAPROSTIL 600 (FARMITALIA®) supplement composed of Serenoa Repens associated with PEA combined with alpha-blocker in the reduction of LUTS symptoms in patients with IBP. During the entire study period, any adverse events, intolerance, allergic reactions, complications related to the products used will be recorded.

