#### 5.3.1 Safety assessment and appearance of adverse events:

An adverse event is considered any unfavorable and unwanted sign, symptom or disease found in a patient participating in a clinical study temporarily associated with the use of an experimental product, even if it does not necessarily have a causal relationship with the treatment received. Clinical and/or pathological conditions present prior to initiation of study treatment are considered adverse events only if they worsen after initiation of study treatment.

Every adverse event that occurred during the execution of the study will be recorded.

In the event of an adverse event, the Investigator will promptly institute the appropriate investigations and therapeutic measures. Any adverse event occurring during the study should be treated according to recognized treatment standards. If necessary, the patient will be withdrawn from the study.

The procedures foreseen by the study do not involve any additional risk for the patient's health.

The Investigator must promptly report, within 24 hours, any adverse event that occurs to patients during the study to the Ethics Committee, to the Promoter, in accordance with the provisions of the law.

In the event of accidents (defined by article 9, paragraph 1 of Legislative Decree 46/97 and by article 11, paragraph 1 of Legislative Decree 507/92) that may have occurred during the project, the reports will be sent to the Office V (Medical Device Supervision) of the DGDFSC (General Directorate of Medical Devices, Pharmaceutical Service and Care Safety) of the Ministry of Health, according to the procedures set out in Meddev 2.12-1 rev 6 year 2009, by the Promoter. The information relating to the accidents will also be sent to the Manufacturer.

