### 5.3.2 Expected Adverse Events

Predicted adverse events include all those events that are expected to occur in association with any routine treatment. No serious adverse events have ever been reported in the literature regarding the use of tamsulosin.

Common effects (<1/10 cases, > 1 100 cases (1-10%)): dizziness, particularly on sitting or standing up. Abnormal ejaculation (ejaculation disorder). This symptom means that the seminal fluid does not leave the body through the urethra but enters the urinary bladder (retrograde ejaculation) or that the volume of seminal fluid is reduced or absent (ejaculation failure). Uncommon effects (>1/1000 cases, <1/100 cases (0.1-1%)): headache, palpitations (heart beats more frequently than normal and is also noticeable), decrease in blood pressure to example rising quickly from sitting or lying down often associated with dizziness, stuffy or runny nose (rhinitis), diarrhoea, nausea and vomiting, constipation, weakness (asthenia), rash, itching and hives.

Rare effects ((>1/10000 cases, <1/1000 cases (0.01-0.1%)): fainting and cases of sudden localized swelling of soft tissues of the body (e.g. of the throat and tongue), difficulty breathing and/or itching and rash (rash), as frequently in an allergic reaction (angioedema).

Very rare effects (<1/10,000 cases (<0.01%)): priapism (painful and prolonged involuntary erection requiring immediate medical treatment).

The most frequent adverse events from the use of tamsulosin were orthostatic hypotension, retrograde ejaculation and ejaculation failure, gastrointestinal disorders [31].

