### 5.3.3 Adverse event reporting period

The adverse event baseline period for this study begins on day 0 and ends 30 days after study completion. All adverse events should be documented in the data collection record (CRF), as well as any other events considered potentially related to the device.

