#### 5.4 Post-treatment evaluation protocol

All the variables will be collected by a co-investigator of [name] team during check-ups at pre-established intervals of 1, 3, 6 and 12 months (T1, T2, T3 and T4 respectively) and will be reported in the specific data collection folder (CRF).

- at 1 month (T1), 3 months (T2), 6 months (T3) and 12 months (T4):
- Personal data: identification number and initials of the patient's name and surname, date of birth, telephone number and e-mail address
- Medical history: IPSS, SF-36
- Physical examination: abdominal, urological including rectal examination
- Uroflowmetry: morphological analysis of the flow curve, Qmax, Volume of urine emptied, RPM).

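### Tolerability is the first secondary outcome and every adverse event must be recorded, but the plan does not say how events are elicited, and no visit lists a baseline or follow-up item for the expected tamsulosin effects.

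*Combined protocol and SAP*

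**What the plan says.** **Outcome.** Section 2.2 lists tolerability first among the secondary outcomes: "Evaluate the tolerability profile of the study therapy, analyzing the side effects". It gives no instrument, visit, grading or arm contrast. The efficacy outcomes in 2.1 and 2.2 name their questionnaires, tests, visits and arms.

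**Duty to record.** Section 2 says that "any adverse events, intolerance, allergic reactions, complications related to the products used will be recorded". Section 5.3.1 defines an adverse event and adds: "Every adverse event that occurred during the execution of the study will be recorded". It counts a pre-existing condition only if it gets worse after treatment starts. Section 5.3.3 directs all events to the CRF and sets the window: "The adverse event baseline period for this study begins on day 0 and ends 30 days after study completion".

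**Visit content.** At T0 (5.2) the list holds general characteristics, current therapy, past history, quality of life, IPSS, physical examination and uroflowmetry. At T1-T4 (5.4) the medical history consists of IPSS and SF-36, followed by "Physical examination: abdominal, urological including rectal examination" and uroflowmetry.

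**Expected events.** Section 5.3.2 places dizziness and abnormal ejaculation in its 1-10% band and states: "The most frequent adverse events from the use of tamsulosin were orthostatic hypotension, retrograde ejaculation and ejaculation failure, gastrointestinal disorders".

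**Analysis.** The variables listed in Section 6 are efficacy measures and covariates; no adverse-event variable appears. A general rule compares qualitative variables between pairs of arms by chi-squared test.

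**The concern.** A duty to record events does not say how they are to be found. If one investigator asks every man about ejaculation and dizziness and another waits for a complaint, the same true rate produces different recorded rates. Some events are particularly exposed: a postural fall in blood pressure without symptoms cannot be recorded unless someone measures it, and sexual effects are easily left unmentioned.

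With no masking described, both parties may know who takes tamsulosin and which effects are expected of it. Differences in asking or answering could then follow treatment. A low event count would be hard to interpret: it could reflect good tolerability, or that nobody asked. A missing baseline cannot be recovered afterwards.

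**Working it through.** **1. Expected effects set against visit content**

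| Effect named in 5.3.2 | Item at T0 (5.2) | Item at T1-T4 (5.4) |
|---|---|---|
| Dizziness (1-10% band) | None | None |
| Abnormal ejaculation (1-10% band) | None | None |
| Blood-pressure fall on rising | No blood pressure listed | No blood pressure listed |
| Any adverse event, general question | None | None |

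T0 does take a history (underlying disease, allergies, current medication, onset and type of symptoms), but nothing in it is aimed at these effects. To decide whether dizziness at T1 is new or worse, one must know its state at T0, and the plan does not secure that information.

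**2. Where reporting could differ by arm.** Section 3 gives PEAPROSTIL plus tamsulosin in Arm 1, PEAPROSTIL alone in Arm 2 and tamsulosin alone in Arm 3. Knowing who takes tamsulosin separates Arm 2 from Arms 1 and 3. It does not by itself separate Arm 1 from Arm 3, which is the primary comparison.

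**3. How many events to expect.** The plan's N was set for efficacy. With a difference of 2, SD 4, two-sided 0.05 and 90% power, n = 2 × [4 × (1.960 + 1.282) / 2]² = 84.06, so 85 per arm and 255 in total. The stated 250 is close to this (power about 0.896 at 83 per arm). No figure is given for tolerability. With 250 / 3 ≈ 83 per arm, the 1-10% band gives 83 × 0.01 = 0.8 to 83 × 0.10 = 8.3 men per event.

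**4. Illustration; every comparator rate and capture share is assumed.** Only the 1-10% band comes from the protocol. Power is the sum of Bin(x; 83, p1) × Bin(y; 83, p2) over all tables significant at two-sided 0.05.

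| Recorded rates | Meaning (assumed) | Uncorrected chi-squared | Fisher's exact |
|---|---|---|---|
| 10% vs 1% | All events captured | 77% | 64% |
| 5% vs 0.5% | Half captured in both arms | 43% | 17% |
| 10% vs 5% | True 10% in both; full vs half capture | 22% | 15% |

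The first two rows show lost power under equal under-capture; they do not measure differential reporting. The third row does: a difference that does not exist would be declared in 22% (chi-squared) or 15% (Fisher) of trials, against a nominal 5%.

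**5. Choice of test.** Under the null, the expected events per arm are 83 × (0.10 + 0.01) / 2 = 4.6 in the first row and 83 × (0.05 + 0.005) / 2 = 2.3 in the second. Both are below the usual minimum of 5, so chi-squared is poorly suited to single events at these rates.

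**6. Internal consistency of 5.3.2.** It puts blood-pressure falls on rising in the 0.1-1% band, then names orthostatic hypotension among the most frequent events. It states "No serious adverse events have ever been reported in the literature regarding the use of tamsulosin", then lists angioedema with difficulty breathing, and priapism needing immediate treatment. These are background statements and do not drive the ascertainment problem, but they need reconciling.

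**The case against.** The strongest reply is that adverse-event collection is planned. Sections 2, 5.3.1 and 5.3.3 oblige the investigator to record every event in the CRF from day 0 to 30 days after completion. Section 5.3.1 sits under the measurements made during treatment, where a co-investigator completes the CRF. The CRF pages are not in the documents and may contain a question. This stands: the gap is an unstated method, not absent collection.

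A reader might infer more than the text supports:

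- **That the trial is open-label.** The protocol never says so. It describes no masking, placebo or dummy, and the arms differ visibly (sachet, tamsulosin, or both), so the inference is plausible but remains an inference.
- **That only spontaneous reports will be captured.** The plan is silent; investigators may ask. Nothing makes them ask alike in all arms.
- **That nothing is asked at T0.** A history is taken; it is simply not directed at the expected effects.
- **That a chi-squared comparison of side effects is planned.** The tolerability item names no contrast and Section 6 lists no adverse-event variable. The general pairwise rule could cover one.
- **That knowledge of allocation biases the main contrast.** Arms 1 and 3 both take tamsulosin, so the argument bears chiefly on Arm 2.

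Section 1 says of herbal products: "Gastrointestinal disturbances are the most common reported". It also describes their side effects as usually mild and similar to placebo. Although 5.3.2 is written for tamsulosin, its list already includes diarrhoea, nausea, vomiting and constipation, so a checklist built from it would cover that category.

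Finally, a checklist equalises the asking, not the answering; it reduces the effect of known allocation but does not remove it.

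**Conclusion.** The concern holds in a limited form. The plan requires events to be recorded but does not state how they are elicited, graded or compared, and no listed visit item targets the expected tamsulosin effects at baseline or follow-up. As written, the first secondary outcome lacks uniform capture, and the worsening rule in 5.3.1 cannot be applied reliably to those effects.

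The size cannot be fixed from the documents. The one firm figure is about 1 to 8 men per arm for each event in the 1-10% band. The power and false-positive figures depend on assumed rates and capture shares, and show direction only. The possibility of arm-dependent reporting rests on reading the absence of any described masking as absence of masking.

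The efficacy outcomes are not affected. The change is worth making before enrolment because the missing baseline cannot be rebuilt later.

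**What to change.** 1. **CRF and Sections 5.2 and 5.4.** Add one fixed yes/no list of the events in 5.3.2, worded identically in all three arms and asked at T0 and at T1-T4.
2. **Section 2.2.** Define the tolerability outcome as the proportion of men with at least one new or worsened listed event since T0, and name the arm pairs to be compared.
3. **Section 6.** Add this variable. Use Fisher's exact test where an expected count is below 5, and the planned chi-squared test otherwise. Report individual events descriptively, so that many events across three arm pairs do not generate a series of unadjusted tests.
4. **Optional.** Measure blood pressure at the existing physical examination. If this is added, the investigators must pre-specify the reading that counts as an event; otherwise symptomless falls would not enter the endpoint.
5. **Section 5.3.2.** Reconcile the two statements on how frequent orthostatic hypotension is, and the statement on serious events with the angioedema and priapism listed after it.
6. **Masking.** State whether patients and assessors are masked.

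The cost is wording in the protocol and CRF, and a few minutes per existing visit. Recorded rates will be higher than with unprompted reporting, and common background complaints such as headache may dilute the composite; the descriptive table of single events addresses this.

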## 3. Study design

The study is a single-center, 3-arm, prospective randomized clinical trial.

- Arm 1: PEAPROSTIL 600 + Tamsulosin 0.4 mg/dl
- Arm2: PEAPROSTIL 600
- Arm 3: Tamsulosin 0.4 mg

Upon enrollment in the study, each patient will be randomized into one of the 3 arms described. Randomization will take place in a 1:1:1 pattern.

Based on clinical-scientific considerations inherent to the typology of patients and to reality clinic, the experimental design indicated above currently corresponds to the best possible.

### 3.1 Composition of the therapy

- PEAPROSTIL 600 is a food supplement based on Palmitoylethanolamide and Serenoa Repens, respectively for each sachet there are 600 mg of PEA and 320 mg of Serenoa oil. The net content of a sachet is 2.45 g and can be orodispersible without the need for the use of water. The drug does not contain gluten or lactose.
- Tamsulosin 0.4 mg is a drug belonging to the category of alpha-blocker drugs used as first choice drugs (according to EAU lines) for the treatment of LUTS/BPH. The recommended dose is 0.4 mg per day (1 administration), to be taken preferably at the same time during the day, indifferently with or without meals.

### 4. Patient selection

#### 4.1 Target population

Patients referred to outpatient visits eligible for study at the S.C.D.U. of Urology of the Maggiore Hospital of Charity of Novara.

#### 4.2 Inclusion criteria

- o Male patients aged 40 years or older
- o Patients with baseline IPSS questionnaire between 8 and 14
- o Patients with prostate volume  $\leq$  60 cc assessed by transrectal ultrasound (TRUS)
- o Patients who have a Qmax  $\leq$  15 ml/sec on uroflowmetry
- o Patients who show a post-voiding residue  $\leq$  120 ml on extemporaneous ultrasound
- o Patients who have signed the informed consent for participation in the study
- o Patients able to understand the conditions of the study and to participate for the full duration.

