Controlled studies show that  $\alpha 1$ -blockers typically reduce IPSS by approximately 30-40% and increase Qmax by approximately 20-25% [17].  $\alpha 1$ -blockers do not reduce prostate size [18]. The most frequent adverse events of  $\alpha 1$ -blockers are asthenia, dizziness and orthostatic hypotension. They do not negatively affect libido, have a small beneficial effect on erectile function, but sometimes cause abnormal ejaculation [19]. Originally, abnormal ejaculation was associated with retrograde ejaculation, but more recent data show that it is due to a decrease or absence of seminal fluid during ejaculation.

Thus,  $\alpha 1$ -blockers are often considered the first-line pharmacological treatment of LUTS due to their rapid action, good efficacy, low frequency and severity of adverse events. However,  $\alpha 1$ -blockers do not prevent the onset of acute urinary retention and the need for surgery for BPH.

Another category of drugs involved in the treatment of BPH are the 5 alpha reductase inhibitors (5-ARIs). The effects of androgens on the prostate are mediated by dihydrotestosterone (DHT), which is converted from testosterone by the enzyme 5 $\alpha$ -reductase. There are two isoforms of this enzyme:

- 5 $\alpha$ -reductase type 1, activity predominant in extraprostatic tissues, such as skin and liver.

- 5 $\alpha$ -reductase type 2, predominant in the prostate.

Two 5-ARIs are available for clinical use: dutasteride and finasteride. Finasteride inhibits type 2 5 $\alpha$ -reductase only, whereas dutasteride inhibits type 1 and type 2 5 $\alpha$ -reductase with similar potency. 5 $\alpha$ -reductase inhibitors work by inducing apoptosis of prostate epithelial cells [20] leading to a reduction in prostate size by approximately 18-28% and a decrease in circulating PSA levels by approximately 50% after six to twelve months of treatment [21].

Placebo-related clinical effects are observed after a minimum treatment duration of at least six to twelve months. An indirect comparison and a direct comparative trial (twelve months duration) indicate that dutasteride and finasteride are equally effective in the treatment of LUTS [21, 23]. The greater the baseline prostate volume, the greater the symptomatic benefit of dutasteride over tamsulosin.

5 $\alpha$ -reductase inhibitors, but not  $\alpha$ 1-blockers, reduce the long-term risk (> 1 year) of acute urinary retention or the need for surgery [22, 24].

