## 5.2 Pre-treatment assessment

All patients will undergo an accurate analysis of the following parameters (T0).

- Personal data: identification number and initials of the patient's name and surname, date of birth, telephone number and e-mail address.
- General characteristics: gender, weight, height, smoker, coffee and/or tea intake, allergies, job, sport, diabetes mellitus.
- Medical therapy in progress.
- Remote pathological history: previous surgical interventions, underlying pathologies and number of deliveries.
- Past pathological history and diagnosis: starting date and type of symptomatology
- Assessment of quality of life (QoL questionnaire).
- Voiding assessment (IPSS questionnaire)
- Physical examination: abdominal, urological including rectal examination.
- Uroflowmetry (morphology of the curve, Qmax, Vol, RPM-residual evaluation post urination)

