#### 6. Sample size and statistical analysis of the data

A total of 250 patients will be recruited. The sample analysis was performed by the "GF Ingrassia" Department of Medical, Surgical Sciences and Advanced Technologies of the University of Catania. In particular, the design foresees a 1:1:1 randomization process in 3 arms. Expect a difference of at least 2 points in IPSS and Qmax and a standard deviation of 4, as described in previous studies (Morgia et al., 2014; Alcaraz et al., 2016), it is necessary to enroll 250 patients to obtain a power 90% statistic at a significance level of 0.05.

The statistical analysis of the data collected during the study, according to an intention-to-treat procedure, will be performed using statistical software such as IBM SPSS statistics version 23.0. The variables that will be collected in order to evaluate the efficacy of the therapy will be: chronological age, weight, BMI, smoking, diabetes, PSA, IPSS, Postvoiding Residual, Qmax, QMed, Voided volume, SF-36 score. A descriptive analysis of the patients included in the three arms will be performed using the appropriate frequency measures and indices of central tendency and dispersion. Considering one pair of the three arms at a time (1 vs. 2; 1 vs. 3; 2 vs. 3), the qualitative variables will be compared using the chi-squared test; the quantitative variables will be

compared using Student's t-test. The level of significance will be set at  $p < 0.05$ . For the variables that will be significant in the univariate analysis, multivariate analyzes will be performed using appropriate regression models to control for the effect of the covariates.

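### TRUS prostate volume is needed from every man at entry, but the plan neither lists it for recording at T0 nor provides for reporting it by arm or adjusting for it

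*Combined protocol and SAP*

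**What the plan says.** **Entry (Section 4.2).** Prostate volume must not exceed 60 cc, "assessed by transrectal ultrasound (TRUS"). The same list sets limits on IPSS, Qmax and post-voiding residue.

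**Baseline record (Section 5.2).** The list opens with "All patients will undergo an accurate analysis of the following parameters (T0"). It contains no TRUS or prostate volume item. The nearest items are "Physical examination: abdominal, urological including rectal examination" and "Uroflowmetry (morphology of the curve, Qmax, Vol, RPM-residual evaluation post urination").

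**Follow-up (Section 5.4).** Prostate volume is not listed. The uroflowmetry item there spells its volume out as "Volume of urine emptied".

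**Analysis (Section 6).** The variables to be collected for evaluating efficacy are "chronological age, weight, BMI, smoking, diabetes, PSA, IPSS, Postvoiding Residual, Qmax, QMed, Voided volume, SF-36 score". Arms are compared in pairs, with Student's t-test for quantitative variables. Regression follows only for variables significant in univariate analysis, and is described as "appropriate regression models to control for the effect of the covariates". No covariate is named.

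**General recording rule (Section 5.1).** Data that the protocol requires go on the paper CRF, and the study variables go into the analysis database.

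**The concern.** Gland size is a basic descriptor of men with benign prostatic hypertrophy, and here it is measured on everyone before randomisation. IPSS, Qmax and residue are also entry measurements, and all three reappear in both the T0 list and the Section 6 list. TRUS volume is the only measured entry criterion that appears in neither, which looks more like an oversight than a choice.

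Three things follow if the lists are implemented as written:

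- The baseline table would not show gland size by arm, so readers could not judge comparability on it.
- The 60 cc limit could not be checked from the analysis database.
- A pre-randomisation measurement that might improve precision would have no planned role in the Arm 1 versus Arm 3 comparison. Any adjustment at all would depend on a univariate significance screen.

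**Working it through.** **Step 1. Where each entry measurement appears.**

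| Entry measurement (4.2) | T0 list (5.2) | Section 6 list |
|---|---|---|
| IPSS | yes | yes |
| Qmax | yes | yes |
| Post-voiding residue | yes | yes |
| Prostate volume by TRUS | no | no |

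The Vol entry in Section 5.2 is not prostate volume. It is a uroflowmetry parameter, and Section 5.4 shows that this parameter is urine volume. Section 6 names 12 variables, and its only volume is voided volume.

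**Step 2. Reproduce the planned sample size.** Inputs from Section 6: difference 2, SD 4, significance level 0.05, power 90%, 250 patients in three equal arms (250/3, about 83 per arm). Two-sided testing is assumed, since the plan does not state it.

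n per arm = 2 × SD² × (z₀.₉₇₅ + z₀.₉₀)² / difference² = 2 × 16 × (1.960 + 1.282)² / 4 = 84.06, rounded up to 85. Three arms give 255, close to the stated 250.

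The exact two-sided t-test at 83 per arm (164 degrees of freedom) has noncentrality 2 / (4 × √(2/83)) = 3.221 and power 89.3%. The normal approximation gives 89.6%. The figures below use the exact t-test.

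**Step 3. What adjustment for volume could add.** Let r be the correlation between TRUS volume and the outcome within arms. The documents give no value, so r is an assumption. The residual SD is 4 × √(1 − r²), and the equivalent gain in sample size is 1/(1 − r²).

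| Assumed r | Residual SD | Equivalent sample gain | Power at 83 per arm |
|---|---|---|---|
| 0 | 4.000 | none | 89.3% |
| 0.1 | 3.980 | 1% | 89.6% |
| 0.2 | 3.919 | 4% | 90.5% |
| 0.3 | 3.816 | 10% | 91.9% |

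**Step 4. The same gain with the baseline outcome already in the model.** What then matters is the partial correlation of volume with outcome given baseline. For illustration, assume a baseline–outcome correlation of 0.5 and a volume–baseline correlation of 0.2:

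partial r = (r − 0.5 × 0.2) / √((1 − 0.5²)(1 − 0.2²)) = (r − 0.1) / 0.849

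- r = 0.2: 0.1/0.849 = 0.118, a sample gain of 1/(1 − 0.0139), or about 1.4%.
- r = 0.3: 0.2/0.849 = 0.236, a sample gain of 1/(1 − 0.0556), or about 6%.

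Under these assumptions, the extra contribution of volume falls from 4–10% to about 1.4–6% of the sample.

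**The case against.** The best counter-argument is that absence from a list is not absence from the trial. Section 5.1 sends all protocol-required data to the CRF, and a TRUS volume is required by Section 4.2. The T0 list is also visibly incomplete: PSA and QMed are missing from it, yet Section 6 says they will be collected. This stands. A reader might infer that gland size will go unrecorded, that the analysis cannot use it, or that an imbalance could never be described or corrected. The documents do not support that. They show only that the plan does not name the variable or give it a role.

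A reader might also take the Section 6 list as the closed set of regression covariates, with volume deliberately left out. Section 6 does not say so. Its list mixes outcomes with patient characteristics, and the covariates are never specified.

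It is tempting, too, to cite the introduction as evidence that volume predicts outcome: "The greater the baseline prostate volume, the greater the symptomatic benefit of dutasteride over tamsulosin". That sentence concerns dutasteride, which is in no arm of this trial. It also describes how a difference between two drugs varies with gland size, which is not the prognostic association that yields precision. It makes volume relevant to report but does not show that adjustment will pay off here.

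Finally, the gain may be very small. Entry limits on volume and on IPSS (8 to 14) tend to weaken correlations. PSA, which the introduction says rises with gland volume, is already on the Section 6 list as a rough proxy. These points stand, and they are why the range in the working starts at r = 0. They reduce the size of the benefit but do not explain why one entry measurement is missing from both lists.

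**Conclusion.** The omission is real and minor. A measurement required of every man at entry is named neither in the T0 list nor among the Section 6 variables, so the plan does not provide for describing it by arm or adjusting for it.

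On the assumed range r = 0 to 0.3, adjustment for volume alone adds between nothing and 2.6 percentage points of power (91.9 − 89.3), with 0.3 points at r = 0.1. With the baseline outcome in the model, the contribution of volume is smaller. These figures rest on assumed correlations, two-sided testing, 83 per arm and no dropout.

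It would be wrong to conclude that the treatment comparison is biased or that 250 patients is the wrong number because of this. Randomisation keeps the Arm 1 versus Arm 3 comparison unbiased without the covariate, and the planned sample does not depend on it. The benefit is a fuller baseline description, an eligibility check from the database and a modest amount of precision.

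**What to change.** - Section 5.2: add 'TRUS prostate volume (cc)' to the T0 list, with a matching CRF field.
- Section 6: add the same variable to the list and include it in the descriptive table by arm.
- Section 6: make the Arm 1 versus Arm 3 comparison of each quantitative outcome a regression (ANCOVA) on treatment arm, with the baseline value of that outcome and TRUS volume as fixed, pre-specified covariates. Keep both in the model whatever their univariate significance.

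Settle this before any comparison by arm, including the preliminary analyses of 3- and 6-month data in Section 7, because a covariate added afterwards is no longer pre-specified.

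The cost is one CRF field and one model term. No new procedure, visit or patient is needed, because the scan is already an entry requirement.
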